If participants have previously (after 1 March 2020 and at least four months before the date of the first sample collected as part of this study) had a blood sample tested for SARS-CoV-2 antibody as part of their routine HIV care or another research study (for which the result is available in their medical records), that test will be considered as the first test for this study. These participants would therefore provide an additional blood sample at only one study visit. Clinical data corresponding to the time of the first sample collection will be extracted.

If participants have previously (after 1 March 2020 and at least four months before the date of the first sample collected as part of this study) had blood taken for other reasons that is still stored, this may also be tested for SARS-CoV-2 antibodies. In these cases, this would be considered the first test for this study and these participants would provide an additional blood sample at only one study visit. Clinical data corresponding to the time of the first sample collection will be extracted.

Participants who are followed in cohorts which are part of the EPPICC network will continue to be followed up through the ongoing EPPICC Paediatric Study.

Table 1: Study participant timeline

	Baseline	2nd visit at 6 months*
Eligibility screen	X	
Informed consent	X	
Blood sample for SARS-CoV-2 antibody	X	X
COVID-19 patient questionnaire	X	X
Clinical data collection	X	X

* Participants who have results available from a previous blood test for SARS-CoV-2 antibody in the previous 4 months (as part of routine care or research) do not require a second test.

Participants will be given the result of their SARS-CoV-2 antibody tests with guidance on how to interpret the results, unless this conflicts with the clinic or study's usual practice.

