3.2 ENROLMENT AND FOLLOW-UP

We aim to start enrolment from November 2020 (pending ethics approval) and enrol participants for approximately twelve months or until the sample size is met. The enrolment period may be extended in the event of disruptions to clinic services due to COVID-19. Where feasible, all children and adolescents meeting the inclusion criteria and attending the participating clinics during this period will be invited to take part; where this is not possible, a convenience sample of children and adolescents (e.g. those attending clinic on a specified day of the week) should be invited. The invitation to participate should be independent of the patient's probability of having been exposed to COVID-19.

Participants will be considered lost to follow-up for the purposes of this study if they have not provided the second blood sample by 13 months after the enrolment date.

Participants enrolled in the EPPICC Paediatric Study or CTAAC will continue to be followed up as part of the ongoing study.

Logs will be kept of the number of children and adolescents declining the invitation to participate, with reasons for refusal where available.

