6 STATISTICAL CONSIDERATIONS

6.1 SAMPLE SIZE

The total sample size is 1150, with provisional numbers eligible by cohort summarised in Table 3. Allowing for 70% participation, the target sample size can be met within the participating cohorts. At some sites within EPPICC, participants will receive SARS-CoV-2 serological tests as part of routine care or within an ongoing research study, and a repeat test will be offered as part of this study approximately six months after (no less than 3 and up to 13 months) the first sample; however both sets of results will be collected in this study. At other sites and in South Africa, both tests will be part of this study.

In addition, some sites may be able to test stored samples taken for other purposes and not previously tested for SARS-CoV-2 antibodies. In these cases, this would be considered the first test and the participant would have one additional test as part of this study approximately six months (no less than 3 and up to 13 months) after the first sample date.

Table 3: Provisional numbers of eligible participants (aged <25 years) per cohort

Cohort	Number of eligible participants	
	CLWHIV	HIV-uninfected adolescents
Belgium	74	0
Greece	22	0
CoRISPES (Spain)	250	0
CoRISPE-Cat (Spain)	50	0
Sweden	85	0
Ukraine	170	0
United Kingdom	442	0
EPPICC Total	1093	0
South Africa	400	50-100
Total	1493	50-100

Assuming an overall anti-SARS-CoV-2 prevalence of 10%, similar to that reported for children aged 10-19 years in Geneva, Switzerland [3], the sample size would result in a 95% confidence interval of +/- 2% in Europe and +/-3% in South Africa.

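### Sections 2.3 and 3.1 set no maximum age for an earlier test or stored sample used as the first test, while section 6.1 requires the repeat test within 13 months of it

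*Combined protocol and SAP*

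**What the plan says.** Two retrospective routes supply a first test without a new blood draw.

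- **Earlier antibody test (section 3.1).** The rule opens "If participants have previously (after 1 March 2020 and at least four months before the date of the first sample collected as part of this" …, which sets a calendar start and a minimum age. Then "that test will be considered as the first test for this study", and the participant gives blood at one study visit only.
- **Stored blood (section 3.1).** The same date condition applies, and "this would be considered the first test for this study and these participants would provide an additional blood sample at only one study visit".
- **Consent (section 2.3).** An earlier test must be at least four months old, and such participants are offered one further test. Stored samples may date from 1 March 2020 onward. Neither route has a maximum age.
- **Sample size (section 6.1).** For an earlier test, the repeat comes "approximately six months after (no less than 3 and up to 13 months) the first sample". For stored blood it comes "approximately six months (no less than 3 and up to 13 months) after the first sample date".
- **Loss to follow-up (section 3.2).** "Participants will be considered lost to follow-up for the purposes of this study if they have not provided the second blood sample by 13 months", counted from the enrolment date.

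Two smaller mismatches concern the same rule. The minimum gap is four months in sections 2.3 and 3.1 but three months in section 6.1. The footnote to Table 1 waives the second test for people with a result from within the previous four months, whereas the text of section 3.1 asks for a result at least four months old.

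**The concern.** A site enrolling in autumn 2021 and holding a participant's sample from spring 2020 meets section 3.1, takes one study sample, and has a pair that section 6.1 does not allow. Because section 3.1 drops the second study sample on these routes, no later planned sample exists to form a pair inside the window.

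Change between the two tests is central to the study. The primary objective includes how prevalence changes over time, and a secondary objective is the incidence of changes in antibody status (section 1.2). If gaps range from a few months to well over a year, a simple proportion changed mixes very different lengths of exposure. Over a long gap a participant can also seroconvert, lose detectable antibody, and be recorded as unchanged. Section 6.2 plans logistic and Poisson regression but states no person-time offset, interval restriction or other handling of unequal gaps.

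**Working it through.** The 13-month limit is a design rule, not a calculated figure, so there is nothing to reproduce. The check is calendar arithmetic.

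**Inputs**
- Earliest first-sample date: 1 March 2020 (section 3.1).
- Minimum age of that sample: 4 months before the first study sample (section 3.1).
- Maximum gap: 13 months (section 6.1).
- Enrolment: from November 2020 for about twelve months (section 3.2), taken here as 1 November 2020 to 1 November 2021.
- Assumption: the single study sample is taken at enrolment.

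**Step 1. Largest gap under section 3.1 alone.** Gap = study-sample date minus 1 March 2020.

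| Study sample | Largest gap (months) |
|---|---|
| 1 November 2020 | 8.0 |
| 1 April 2021 | 13.0 |
| 18 May 2021 (date of version 3.0) | 14.6 |
| 1 November 2021 | 20.0 |

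The limit can be exceeded only after 1 April 2021, which covers 7 of the 12 planned enrolment months. At the planned end the excess is up to 20 − 13 = 7 months.

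**Step 2. Share of permitted dates that breach the limit.** Let T be the months from 1 March 2020 to the study sample. Section 3.1 permits a span of T − 4 months of first-sample dates. For T above 13, the oldest T − 13 of those months break the limit. The share is (T − 13)/(T − 4).

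- T = 13 (1 April 2021): 0/9 = 0%.
- T = 15 (1 June 2021): 2/11 = 18%.
- T = 20 (1 November 2021): 7/16 = 44%.

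**Step 3. Average over planned enrolment.** Assume retrospective pairs arise at a constant rate from T = 8 to T = 20, with first-sample dates spread evenly over the permitted span:

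(1/12) × ∫ from 13 to 20 of (T − 13)/(T − 4) dT = (1/12) × [7 − 9 ln(16/9)] = (1/12) × (7 − 5.18) = 0.15.

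About 15% of retrospective pairs would fall outside section 6.1.

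**Step 4. Does another rule catch these pairs?** The 3-to-13-month window that section 3.1 gives for the standard two-visit schedule runs from study entry. The limit in section 3.2 runs from enrolment. Section 7.3 closes the study once each participant has two analysed samples or is lost. None of these measures the age of an earlier sample.

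**Step 5. What would the 13-month limit leave in place?** A sample from early March 2020 paired with a study sample on 1 November 2020 has a gap of about 8 months and meets every rule. Such a sample stays acceptable for study samples up to 1 April 2021.

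**The case against.** The strongest reply is that the limit is already written down. Section 6.1 applies it to both retrospective routes and counts it from the first sample. All the rules can be met together: after 1 March 2020, and between 4 and 13 months before the study sample. A reader might infer that the protocol has no maximum at all; it does, and gaps of 20 months arise only if section 3.1 is followed without section 6.1. That stands, and it makes this a conflict between sections. The conflict still matters, because section 3.1 is the procedural section, and no section says what to do when the only earlier sample is too old.

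A reader might also infer that early-2020 baselines inflate the estimated change and that the limit would cure this. The documents do not show it. A low prevalence in spring 2020 may be correct for its date, and step 5 shows that many such samples satisfy the limit. The spread of baseline dates comes from the 1 March 2020 start.

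Nor do the documents declare an overlong retrospective pair complete. Section 3.2 does not address such pairs, and section 6.1 puts them outside the window.

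It is fair, too, that test dates are collected (Table 2) and that Poisson regression can use person-time. That could handle part of the unequal exposure if it were specified. It would not recover seroconversions that reversed between the two samples.

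Finally, version 3.0 was edited partly to admit vaccinated participants who had an antibody test before vaccination (section 14). Discarding their older results would lose information, so any fix should keep them.

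**Conclusion.** The point holds as an inconsistency to be reconciled. Sections 2.3 and 3.1 admit first tests that section 6.1 excludes, for study samples after 1 April 2021 and with gaps up to about 20 months by 1 November 2021. They then remove the second study sample that would give an in-window pair.

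The size is about 15% of retrospective pairs, assuming enrolment on plan, a constant rate, evenly spread first-sample dates and the study sample taken at enrolment. The 44% applies only to the last planned enrolment day. It is a share of calendar dates, so it should not be read as a share of participants. The documents do not say how many participants will use these routes; section 6.1 refers only to some sites. Enrolment may stop early or be extended (section 3.2), which would lower or raise these figures.

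The harm is limited to the change-in-status analyses: very unequal intervals pooled together, and reversals missed within long gaps. Bias in baseline prevalence is not established.

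**What to change.** 1. In section 2.3 and in both retrospective paragraphs of section 3.1, state that an earlier test or stored sample is the first test only if taken no more than 13 months before the study sample, as section 6.1 already requires.
2. If the only earlier result is older than that, keep it as additional historical data, including any pre-vaccination result, and put the participant on the standard two-sample schedule.
3. State one minimum gap for these routes in sections 2.3, 3.1 and 6.1 (now four months or three), and align the Table 1 footnote with the text.

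A rule for choosing among several eligible stored samples, such as the one nearest six months, would be tidy but is optional.

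**Cost.** This is a protocol amendment; if judged substantial, section 14 requires agreement from the investigators, the sponsor and the ethics committee. The consent section needs an edit. It speaks of samples at up to two time points, but it also says that people with an earlier test are offered one more, so it does not plainly cover a second study sample for them. Participants affected give one more sample and questionnaire at a routine visit. For late enrolees, the first in-window sample may fall after vaccination, which is why the older result should stay in the dataset.

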2.3 INFORMED CONSENT

Participants and, where necessary, their parents / carers will be asked for informed consent before taking part in the study.

Children / adolescents and their parents / carers (as appropriate) will receive a Participant Information Sheet detailing study procedures, together with a Consent Form. To participate in the study, participants will need to:

- Agree to give a blood sample at up to two different time points, for testing for SARS-CoV-2 antibody. Participants who have previously received an antibody test as part of standard care or a research study in their clinic at least 4 months ago will be offered one additional test.
- Agree for the site investigator to determine whether the local laboratory has any stored blood samples for the participant (taken on or after 1 March 2020) and for any such samples to be tested for SARS-CoV-2 antibody
- Complete a short questionnaire at up to two different time points
- Agree to the research team collecting clinical data including on their HIV if applicable (e.g. treatment status, CD4 counts and viral loads)
- Agree to record linkage to data collected in ongoing studies in which they may be participating (e.g. EPPICC, local or national HIV cohort studies and / or local or national COVID-19 studies).

Consent may be given in person or, if clinics are operating remotely, consent may be provided via phone or video call if permitted under local guidelines and approvals.

Participants may withdraw from the study at any time without giving a reason.

Patients not consenting to participate will continue to receive their usual care in routine follow-up at the clinic. If a patient chooses not to participate in the study or subsequently withdraws, there will be no impact on their clinical care.

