3 STUDY PROCEDURES

3.1 STUDY DESIGN

This is a serial point prevalence survey of representative samples of children and adolescents attending routine HIV care in the participating clinics and cohorts, with repeat antibody testing at baseline (study entry) and approximately 6 months after study entry (Table 1), and in some clinics further long-term follow-up through linkage to data collected in an ongoing longitudinal cohort study. In South Africa approximately 50-100 HIV-uninfected adolescents enrolled in the ongoing CTAAC cohort will be invited to participate in this study as a comparator group.

Eligible participants who are interested in joining the study will be asked for their consent to participate if aged ≥ 16 years or as per local legal requirements. For participants aged <16 years, consent of their parent/carer will be sought as per legal requirements. Assent will be sought from children and adolescents aged 10 years and older, depending on local ethics requirements. Potential participants and their parents / carers should be allowed at least 5-10 minutes to consider whether or not to take part; where possible, it may be helpful to give patients copies of the participant information sheet while they wait for their appointment.

Data collection will be conducted at HIV clinics during routine visits in clinical care (in the European cohorts) or planned study visits (in CTAAC, for both CLWHIV and HIV-uninfected adolescents), and no additional study visits will be required.

At entry to the study the participant will give a venous blood sample for a SARS-CoV-2 antibody test (the exact test used will depend on local clinical practice). An additional serum sample will be taken at the same time as a routine blood draw and leftover sample will be used if possible. At the next scheduled routine HIV clinic/study visit approximately 6 (no less than 3 and up to 13) months later, a repeat venous blood sample will be collected for a second antibody test. At each visit, participants (or their parents/carers) will be given a COVID-19 questionnaire, asking short questions about any COVID-19 diagnoses in themselves or among household members and other possible exposures to the virus. All study procedures will be carried out following local COVID-19 guidelines.

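### The Table 1 footnote waives the second antibody test after a recent result, which conflicts with the at-least-four-months rule in 2.3 and 3.1 and allows pairs closer than the 3-month minimum

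*Combined protocol and SAP*

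**What the plan says.** Section 3.1 describes a survey "with repeat antibody testing at baseline (study entry) and approximately 6 months after study entry". The repeat sample has a window: "approximately 6 (no less than 3 and up to 13) months later, a repeat venous blood sample will be collected". Section 6.1 gives the same 3-to-13-month window, and applies it expressly to participants whose first test came from routine care, another study or a stored sample.

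The body of 3.1 also says when an earlier test may stand in for a study sample. It must have been done "after 1 March 2020 and at least four months before the date of the first sample collected as part of this study", and then "that test will be considered as the first test for this study", so that only one study sample is taken. The same condition is set for stored blood. Section 2.3 agrees for earlier tests: a person tested "at least 4 months ago will be offered one additional test".

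The footnote to Table 1, marked by an asterisk on the 6-month visit column, differs. Participants with a result "in the previous 4 months (as part of routine care or research) do not require a second test". It gives no reference date for the 4 months.

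**The concern.** The body text accepts an earlier result when it is four months old or more. The footnote grants its waiver when the result is four months old or less. Table 1 is the participant timeline, so a site may well work from it. Two sites could each follow the protocol and sample the same kind of participant differently.

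The situation can arise in practice. Section 6.1 states: "At some sites within EPPICC, participants will receive SARS-CoV-2 serological tests as part of routine care or within an ongoing research study".

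What is at stake is the paired information. Section 1.2 makes change in prevalence over time part of the primary objective, and the incidence of changes in antibody status a secondary one. A site that follows the footnote may omit a planned second sample and supply instead a pair too close together to say much about change. Once the follow-up window has closed, that sample cannot be obtained.

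**Working it through.** The plan gives no figure on this point to reproduce. The check is interval arithmetic on the plan's own windows.

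**Inputs**
- Footnote window: result 0 to 4 months old (Table 1).
- Rule for earlier tests: at least 4 months old (2.3, 3.1).
- Gap between the two samples: 3 to 13 months, about 6 planned (3.1, 6.1).
- Assumption, not in the documents: result dates are spread evenly over the footnote window.

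**Reading 1: the 4 months count back from the entry sample.** The gap equals the age of the earlier result, so it runs from 0 to 4 months.
- Share under 3 months: 3/4 = 75%.
- Mean gap: (0 + 4)/2 = 2 months, against 6 planned.
- Apart from exactly 4 months, no such pair meets the rule in 2.3 and 3.1.

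Two cases show the reversal:
- *Result 2 months before entry.* Under 2.3 and 3.1 it is not accepted as the first test, so two study samples are due. Under the footnote the second is waived, leaving a 2-month pair.
- *Result 6 months before entry.* Under 2.3 and 3.1 one study sample is due. The footnote gives no waiver, so Table 1 asks for two.

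**Reading 2: the 4 months count back from the second visit, at month V.** A recent outside result replaces the second sample. The gap runs from max(0, V − 4) to V.

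| Second visit (month V) | Gap allowed (months) | Share under 3 months |
|---|---|---|
| 4 | 0 to 4 | 3/4 = 75% |
| 5 | 1 to 5 | 2/4 = 50% |
| 6 | 2 to 6 (mean 4) | 1/4 = 25% |
| 7 | 3 to 7 | 0 |

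From month 7 onwards there is no breach. This reading is a different rule from 2.3 and 3.1, not their reverse, but no other part of the protocol describes it.

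**Effect on time between tests.** The loss per affected pair, against 6 months, is:
- Reading 1: 1 − 2/6 = 66.7%.
- Reading 2 at month 6: 1 − 4/6 = 33.3%.

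The share of pairs affected is not in the documents, so a range is assumed. Each entry is the share multiplied by the loss per pair.

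| Share of pairs affected | Reading 1 | Reading 2, month 6 |
|---|---|---|
| 5% | 3.3% | 1.7% |
| 10% | 6.7% | 3.3% |
| 20% | 13.3% | 6.7% |

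**Effect on the estimates.** A rate per person-time loses precision but is not diluted, because the short gap also shortens the denominator. A simple proportion changed, or a logistic model without a term for the interval, is diluted. Section 6.2 names logistic and Poisson regression but does not say how the interval enters.

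**A smaller mismatch.** For earlier-tested and stored-sample participants the minimum is 4 months in 3.1 (and in 2.3 for earlier tests) but 3 months in 6.1. Both are met at 4 to 13 months; they differ only between 3 and 4.

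**The case against.** The best defence is that the footnote says nothing about spacing, while the 3-to-13-month window is stated without exception in 3.1 and repeated in 6.1 for exactly these participants. Read together, a recent result could stand in only when the window is met. The body rule is stated consistently, so the footnote looks like a wording slip. This may well be its origin, but a site has to infer it: the footnote carries no such condition, and supplying one only restates the conflict.

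A further reading is that the second test means a second *study* test, so that one study sample is taken, timed 3 to 13 months after the earlier result. That would produce no short pair. It does not fit the table, where the asterisk is on the second-visit column and the baseline sample stays marked.

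Several points do stand:
- The footnote does not forbid a sample, and one could still be taken until loss to follow-up is declared at 13 months after enrolment (3.2). The loss is final only after that.
- The number affected is unknown and could be near zero.
- Gaps vary from 3 to 13 months by design, so the need to account for the interval in 6.2 exists with or without the footnote.

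These limit the size of the problem but leave the contradiction in place.

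**Conclusion.** The concern holds. The footnote does not match 2.3 and the body of 3.1, and on both readings that fit the table it allows pairs below the plan's own 3-month minimum. On the first reading this is any result less than 3 months old. On the second it occurs only when the second visit falls before month 7, which includes the nominal 6-month visit.

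The likely effect is modest unless use of recent results is common: across the assumed 5% to 20% of pairs, 1.7% to 13.3% of planned time between tests, depending on the reading. The contradiction itself rests on no assumption. The percentages rest on evenly spread result dates and an assumed share of pairs. Baseline prevalence and the precision figures in 6.1 do not depend on it. The footnote should be corrected because it is an operating instruction that bears on the primary objective.

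**What to change.** Reconcile the Table 1 footnote with 2.3, 3.1 and 6.1 into one rule, with one minimum and one maximum gap counted from the date of the first sample, covering earlier, stored and prospective samples alike. State explicitly whether a recent routine or research result may replace the second-visit sample. Which interval applies is for the study team to decide; the need is for one answer throughout, including the 4-month and 3-month minimums. Section 3.2 counts its 13 months from enrolment, while 6.1 counts from the first sample, so that should be aligned too.

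In 6.2, add a sentence saying that the change analyses use the actual test dates, as a person-time offset or an interval term, with restriction to pairs inside the window as a sensitivity analysis.

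The cost is a corrected footnote, matching sentences in the affected sections, and a notice to sites. Section 7.2.1 says amendments go for further ethics review, so the change could travel with the next amendment, with the site notice sent as soon as approvals permit. Date of test is already collected (Table 2), so no new data are needed, and the fix does not require discarding pairs already obtained.
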